Despite the known effectiveness of buprenorphine sublingual (BSL) maintenance treatment, retention and continued non-prescribed opioid use remain significant limitations. Two recent large trials comparing BSL to other OUD pharmacotherapies found that around 50% or more of patients treated with BSL dropped out of treatment by 3 to 6 months. The first long-acting injectable buprenorphine (Sublocade™) became commercially available in 2018 after receiving an FDA Fast Track and Priority Review designation. This monthly buprenorphine formulation, which is available in two doses (100 mg and 300 mg), can achieve serum buprenorphine concentrations in excess of that achieved by BSL 24 mg per day. Moreover, if an unexpected drug holiday is experienced, at two weeks past the injection due date, μ -opioid receptor remains above 70%, providing some measure of protection against relapse to opioid use. While the Sublocade™ buprenorphine extended-release (BXR) injection product has not yet been compared to BSL treatment for the treatment of OUD, the pharmacologic advantages of BXR can be expected to improve treatment retention and outcome. The extended-release injection aspect should improve compliance and reduce relapse by providing more continuous buprenorphine serum levels as compared to the sublingual formulation. We hypothesize that the BXR injection will have particular benefit for individuals using fentanyl analogues and other HPSO because by providing continuous therapeutic serum buprenorphine levels there will be substantially less opportunity for non-compliance and relapse. Even in the case of a delayed injection, therapeutic levels of buprenorphine will be present for up to two weeks.

We propose an open-label, uncontrolled pilot study, in which patients seeking treatment for OUD who are positive for fentanyl analogues at screening (N = 10) will be inducted onto BSL and then receive BXR injection, with a primary outcome comparison of end of study opioid use compared to baseline. To our knowledge, this would be the first trial to examine the use of this BXR injection formulation for the treatment of OUD patients positive for fentanyl analogues, and the first pharmacotherapy trial of any agent for the treatment of patients with OUD testing positive for HPSO.

Specific Aims and Hypotheses

Specific Aims and Hypotheses

Aim 1: To determine if BXR injection using standard dosing is a feasible treatment for patients with OUD who are positive for HPSO.

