Study Days 1-3: Buprenorphine induction: Study procedures will begin with all participants being inducted onto BSL. For buprenorphine to be safely administered, participants must be in withdrawal from opioids. Individuals will be instructed to abstain from opioids starting at consent and begin buprenorphine medication the day after consent. The day after consent, patients will return to the STARS clinic and be administered a Clinical Opiate Withdrawal Scale (COWS). If found to be in mild withdrawal (COWS score > 6), participants will be started on buprenorphine 2 mg followed by further doses of buprenorphine up to 8 mg on day 1. Because HPSO use may lead to a delayed onset of opioid withdrawal syndrome, the first day that buprenorphine is administered may not be up to three days after a participant's last opioid use.

Whichever day the first dose of BSL is administered will be considered the first day of the induction. The buprenorphine dose will be advanced to a target dose of 24 mg per day on a fixed-flexible schedule, with stabilization at a lower dose if the patient does not tolerate side effects at higher doses. Adequate dosing of buprenorphine is important to its effectiveness, and 16 mg to 24 mg per day is considered the target according to most guidelines.

COMFORT MEDICATIONS: Participants will be given comfort medications to help manage their withdrawal for the first two weeks of the treatment study as needed. Comfort medications prescribed will be

clonidine, clonazepam, prochlorperazine, and zolpidem. Participants will be told that medications may cause some side effects such as sleepiness, lowered blood pressure (which may produce dizziness or a tendency to feel faint), or upset stomach. Participants will be instructed that they should use caution when driving a vehicle or operating appliances or machinery during this time.

Study Day 4: Participants will receive BXR under open-label conditions.

Maintenance Buprenorphine Dosing with BXR treatment: After successful induction onto sublingual buprenorphine, participants will receive BXR (Sublocade) 300 mg subcutaneous injection as per FDA—approved prescribing instructions. The second injection of Sublocade 300 mg will be administered 28 days later. The third injection will occur 28 days subsequent to the second injection at a dose of 100 mg.

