Risks of buprenorphine (BXR and BSL): Addiction, abuse, and misuse are important risks of buprenorphine: Buprenorphine can be abused in a manner similar to other opioids. Life-threatening respiratory depression and death have occurred in association with buprenorphine. There is a potential danger of self-administration of benzodiazepines or other CNS depressants while under treatment with buprenorphine. There is a risk of opioid withdrawal with abrupt discontinuation: Buprenorphine treatment is associated with a risk of hepatitis. Adverse reactions commonly associated with buprenorphine are constipation, headache, nausea, vomiting, increased hepatic enzymes, and fatigue. There is an increased risk of opioid withdrawal symptoms if the medication is initiated too soon after last opioid dose. Buprenorphine has a risk of opioid related side effects--e.g. nausea, constipation, sedation, respiratory depression (particularly when combined with alcohol or other sedating drugs); worsening of opioid use disorder if the medication does not prove effective or is discontinued by the patient, including functional impairment as well as risk of death from drug overdose.

Risk associated with the combination of buprenorphine and other opioids: There is also the possibility of unexpected reaction if patient's in the study use street opioids or other illicit drugs along with buprenorphine. This risk will be mitigated through weekly medical follow-up with patients throughout the study at medication management sessions which will include a formal assessment for adverse events at each medication management visit. Should unexpected adverse events occur, the study physician will use clinical judgement and shared decision making with the patient to determine the best course of action including lowering or discontinuing buprenorphine.

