In order to minimize the risk associated with the study, subjects undergo a comprehensive medical and psychiatric evaluation during the screening procedure. The baseline medical evaluation consists of a physical examination, blood chemistry profile (including liver function tests), complete blood count, urinalysis, serum pregnancy test, urine toxicology and is designed, along with the clinical history, to detect chronic and/or unstable medical illnesses. A comprehensive psychiatric assessment is performed during the screening process, and is intended to detect and assess all past and current psychiatric disorders. The eligibility criteria (see above) are designed to minimize the medical and psychiatric risks to participants by excluding those for whom participation would place them at an increased risk. Special attention will be given to patient's concurrent use of medications. Participants on medications that meet exclusion criteria will not be included in the study.

2) Study Procedures

Participants will be informed about the possible side effects and risks (listed above) of taking BXR or BSL both alone and in combination with other medications, alcohol, or illicit drugs through extensive discussions with staff psychiatrist(s) during the consent process. Participants will be monitored closely with urine drug tests and collecting use episodes each time they attend the clinic. If relapse occurs participants will be given referrals for methadone, buprenorphine maintenance, or inpatient detoxification and follow-up treatment if deemed necessary.

Participants will be told to contact the clinic if they experience any adverse effects and given the number for the 24-hr physician on-call. All participants, both those not taking and taking concurrent medications, will be monitored closely throughout the study for possible signs and symptoms of intoxication and potential for medication misuse. Participants' mental status and physical health are monitored weekly during the study period by a psychiatrist. Vital signs will be obtained at each study visit. At clinic visits, a physician will assess participants for signs and symptoms of adverse effects of buprenorphine, noting which if any symptoms are present, the severity of the symptoms, make adjustments to study medication dose, discontinue study medication, or withdraw participant(s) from the study if needed.

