Study: # 7764 entitled An Open-Label Pilot Study of Sublocade as Treatment for Opiate Use Disorder

PI: [name]
NCT# NCT03861338
Data Analysis Plan created 2-25-2019

C. DATA MANAGEMENT AND ANALYSIS

C1. Data Acquisition and Transmission

All data will be obtained specifically for research purposes. Data will be entered into an Excel spreadsheet coded with a unique identifier assigned to each participant. Departmental, HIPAA-compliant Research Subject Registration System, will however contain participants' names.

C2. Data Entry Methods

As noted above, data will be entered into an Excel spreadsheet. Data management will include: 1) protocol management; 2) patient scheduling; 3) regulatory reporting and 4) management of research organizations, personnel, and collaborators. The research staff will collect and input data on a daily, basis to reduce the likelihood of errors. Information collection and analysis and study-specific data collection will be easily retrievable, organized, and reviewed on an ongoing basis as well.

C3. Data Analysis Plan

Overview of Data Analytic Plan

Sample size: A total of 10 participants will be recruited.

A total of 10 patients will be recruited over a 6-month period. The main analyses in this study will be on the intent-to-treat (ITT) sample, i.e. on all enrolled patients who receive study medication, and all tests will be two-sided, performed at significance $\alpha=0.05$, except where noted. Before specific statistical techniques are applied in order to test the hypotheses of interest, we will examine all variables at all time points for outliers. The distributions of all continuous variables will be checked for normality, and transformations will be employed, if necessary, before applying specific parametric techniques.

Hypotheses testing:

Primary Outcome: The proportion of participants successfully inducted onto BXR.

Secondary Outcomes: BXR treatment will be associated with decreased opioid use for OUD patients positive for HPSO. The primary outcome measure will be opioid use during the last two weeks of the study compared to baseline as measured by a combination of urine toxicology and self-report. BXR injection will be associated with reduce symptoms of craving and symptoms of withdrawal as compared to baseline.

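### The SAP's primary outcome stops at induction, so no listed outcome measures the three-injection, 12-week treatment whose feasibility Aim 1 asks about

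*SAP*

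**What the plan says.** **The aim.** The protocol (Specific Aims and Hypotheses) states Aim 1 as: "To determine if BXR injection using standard dosing is a feasible treatment for patients with OUD who are positive for HPSO".

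**The treatment.** Under Study Procedures, sublingual induction takes Days 1-3. Then: "Study Day 4: Participants will receive BXR under open-label conditions". The second injection follows 28 days after the first and the third 28 days after the second, at 300, 300 and 100 mg. The Lay Summary gives a 12-week study and the same sequence.

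**The rationale.** The Background names retention as a weakness of sublingual buprenorphine and argues that "the pharmacologic advantages of BXR can be expected to improve treatment retention and outcome".

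**Completion.** Description of Subject Population gives 5 as the number of completers needed for the aims, from 10 enrolled.

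**The outcomes.** The SAP (C3, Hypotheses testing) gives the primary outcome as "The proportion of participants successfully inducted onto BXR". It states no definition, time point, threshold or denominator specific to that outcome. The main analyses use enrolled patients who were given study medication. The SAP's secondary outcomes are opioid use over the final two weeks against baseline, craving and withdrawal. The protocol makes late opioid use primary. The SAP lists it as secondary but, in the same paragraph, still labels it the primary measure.

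**The concern.** The aim concerns a course of treatment and the primary outcome concerns its start. On the plain reading, nothing that happens after the first injection can change the primary result. A participant who leaves in week 2 and one who receives all three injections count the same.

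This matters for two reasons. The case for BXR over sublingual treatment is largely about keeping patients in treatment, and no listed outcome would show whether that happened. The pilot is also meant to support a controlled trial, whose planning needs the proportion completing the schedule and the proportion retained. A high induction rate could be reported as feasibility of the 12-week treatment without either figure beside it.

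The denominator adds a second difficulty. If study medication means BXR, the SAP's analysis set contains only people who have already had BXR, and the induction proportion is 100% by construction.

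**Working it through.** Neither document gives a power or precision calculation, so there is no derivation of the sample size to reproduce. The one available check is consistency: 10 enrolled for 5 completers implies non-completion of 1 - 5/10 = 50%, and 5 / (1 - 0.5) = 10.

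**1. When each quantity is known**

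| Event | Timing | Counted by a listed outcome? |
|---|---|---|
| First injection | Day 4 | Yes, the SAP primary (plain reading) |
| Second injection | Day 4 + 28 = Day 32 | No |
| Third injection | Day 32 + 28 = Day 60 | No |
| Opioid use, weeks 11-12 | Last two of 12 weeks | Yes, but counts neither injections nor attendance |
| Still attending at week 12 | 12 x 7 = Day 84 | No |

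**2. What the primary outcome can show with n = 10** (exact Clopper-Pearson 95% intervals)

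- All inducted, 10/10: 100%. The lower limit is 0.025^(1/10) = 0.692, so the interval is 69.2% to 100%.
- Completion if only the 5 required completers remain, 5/10: 50%, interval 18.7% to 81.3%.

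Both can be true of the same 10 people. The SAP primary reports only the first.

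**3. How likely a gap is.** The documents give no rate for reaching the third injection, so it is assumed and varied. With all 10 inducted and each having probability q of reaching the third injection, the number who do is binomial(10, q):

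| q (assumed) | P(fewer than 5 of 10) | P(none of 10) = (1 - q)^10 |
|---|---|---|
| 30% | 0.85 | 0.028 |
| 50% | 0.38 | 0.001 |
| 70% | 0.05 | below 0.00001 |

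The primary outcome is 100% in every row.

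**4. The denominator.** Suppose 10 enrol, all start sublingual buprenorphine, and 8 reach the first injection (illustrative). Over all enrolled, induction is 8/10 = 80% (exact 95% CI 44.4% to 97.5%). If the analysis set means those given BXR, it is 8/8 = 100%, and no result other than 100% is possible.

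**The case against.** **Induction is a sensible hurdle to measure.** The protocol notes that withdrawal may be delayed in users of highly potent synthetic opioids, so getting such patients as far as an injection is itself uncertain. In a pilot of 10, choosing it is defensible. This stands as a reason to keep induction, but not as a reason to let it alone represent the treatment.

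**The plan does look beyond Day 4.** The protocol ties its aims to 5 completers and makes late opioid use its primary outcome, which the SAP retains. This stands in part: that outcome bears on weeks 11-12. It still counts neither injections nor attendance, and the SAP never uses the completer figure.

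**The term is undefined.** A definition of successful induction that required later injections would remove the problem. Neither document gives one, and the protocol uses the word for the sublingual step before the first injection.

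**Departures would be recorded.** Missed doses, and the action taken for side effects, are to be documented. But recording them is not reporting them as an outcome, and the other compliance measure named, pill counts, cannot register an injection given in clinic.

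**Stronger readings that the documents do not support:**

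- A reader might infer that dosing is contradictory, because the risk sections allow "including lowering or discontinuing buprenorphine" and allow the physician to "make adjustments to study medication dose". The first applies when unexpected adverse events occur and the second only where needed. Study medication may also include the sublingual product, which has a flexible schedule. These are conditional safety provisions, and no contradiction with the planned injections is shown.
- A reader might picture 100% success with no one receiving a second injection. The definition permits it, but the probabilities above show that it is remote at plausible rates.
- A reader might conclude that most participants are expected to leave. The protocol's dropout figure of about 50% or more by 3 to 6 months is background from trials of sublingual buprenorphine, and the protocol expects BXR to do better. The 10-to-5 projection implies half, not most.

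**Conclusion.** The concern holds. On its plain reading the SAP's primary outcome is fixed at about Day 4, and neither document lists an outcome for the rest of the schedule or for retention. The primary result alone therefore cannot answer Aim 1. At the protocol's own minimum of 5 completers from 10, the primary could read 100% (69-100%) while completion is 50% (19-81%).

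This rests on two readings: that induction onto BXR means receipt of the first injection, and that the SAP's induction line is the primary outcome although the same section gives that label to late opioid use as well. The 50% is taken from the enrolment projection for illustration and is not a stated dropout assumption. The point limits what the pilot can conclude about feasibility; it does not invalidate the induction result.

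**What to change.** In the SAP, section C3:

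1. Define induction onto BXR, for example as receipt of the first injection, with all enrolled participants as the denominator. State what study medication means in the analysis-set definition.
2. Add two descriptive feasibility outcomes over all enrolled participants, with exact 95% intervals: (a) the proportion receiving all three scheduled injections, with dose changes and missed injections listed separately with reasons; (b) the proportion still attending at week 12.
3. Base the feasibility conclusion on all three proportions.
4. Reconcile the protocol and SAP on which outcome is primary.

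Items 1 to 3 are SAP wording; item 4 may also need a protocol edit. No new visits or tests should be needed: injections are given in clinic, dispensing is checked by participant and study week, and visits are paid individually. That injection and attendance dates are captured is an inference, since the assessment table is a separate attachment not in the documents reviewed. The downside is that reported feasibility may look less favourable than an induction rate alone, and with 10 participants all three intervals will be wide.
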